3.3 SELECTION OF TRIAL POPULATION

Patients in this long-term open label extension trial will be rolled-over after participating in a parent induction trial with spesolimab.

Patients must have tolerated treatment in the parent trial and have completed the treatment period. They must be willing to continue long term treatment with spesolimab for up to 7 years.

A log of all patients enrolled into the trial (i.e., who have signed informed consent) will be maintained in the Investigator Site File (ISF) irrespective of whether they have been treated with the investigational drug or not.

3.3.1 Main diagnosis for trial entry

Patients with fistulising Crohn's disease who have completed treatment in the parent trial.

Please refer to [Section 8.3.1](#) (Source documents) for the documentation requirements pertaining to the in- and exclusion criteria.

3.3.2 Inclusion criteria

Each patient must meet all of the following inclusion criteria to be included into the trial:

1. Patient older than 18 years
2. Has completed all treatments (placebo or active treatment) and the EOT visit in the parent induction trial in fistulising CD and is willing and able to continue treatment in 1368-0007.

3. Has obtained an individual health benefit, per investigator judgement (such as fistula response or remission or other clinical improvement), from treatment in the parent trial.
4. Signed and dated written informed consent for 1368-0007 in accordance with GCP and local legislation prior to admission into the trial.
5. Women of childbearing potential (WOCBP) must be ready to use highly effective methods of birth control per ICH M3 (R2) that result in a low failure rate of less than 1% per year when used consistently and correctly. A list of contraception methods meeting these criteria is provided in the patient information.

Note: A woman is considered of childbearing potential (WOCBP), i.e. fertile, following menarche and until becoming postmenopausal unless permanently sterile. Permanent sterilisation methods include hysterectomy, bilateral salpingectomy and bilateral oophorectomy. Tubal ligation is NOT a method of permanent sterilisation. A postmenopausal state is defined as no menses for 12 months without an alternative medical cause.

3.3.3 Exclusion criteria

Patients meeting any of these exclusion criteria must not be enrolled into the trial:

1. Have experienced treatment-limiting adverse events during induction treatment with study drug.
2. Have developed any condition which meets the exclusion criteria from the original induction study.
3. Any condition which in the opinion of the investigator affects the safety or ability to participate in this trial.

3.3.4 Withdrawal of patients from treatment or assessments

Patients may discontinue trial treatment or withdraw consent to trial participation as a whole (“withdrawal of consent”) with very different implications; please see [Sections 3.3.4.1](#) and [3.3.4.2](#) below.

The decision to discontinue trial treatment or withdraw consent to trial participation and the reason must be documented in the patient files and CRF. If applicable, consider the requirements for Adverse Event collection reporting (please see [Sections 5.2.6.2.1](#) and [5.2.6.2.2](#)).

3.3.4.1 Discontinuation of trial treatment

An individual patient will discontinue trial treatment if:

- The patient wants to discontinue trial treatment, without the need to justify the decision.
- The patient has repeatedly shown to be non-compliant with important trial procedures and, in the opinion of the investigator and/or sponsor representative, is not willing or able to adhere to the trial requirements in the future.
- A patient treated for a luminal inflammatory flare or fistula relapse meets one of the criteria for discontinuation as described below.
- The patient needs to take concomitant medication that interferes with the investigational medicinal product or other trial treatment. Please refer to [Section 4.2.1](#) and [4.2.2](#).
- The patient needs surgical interventions for CD including any fistula surgical procedures (except seton drainage, see [Table 4.2.1.2:1](#))
- The patient can no longer receive trial treatment for medical reasons (such as surgery, adverse events, other diseases, or pregnancy).
- The patient is required to stop treatment due to a specific adverse events as described in [Section 4.2.1](#)

If new efficacy/safety information becomes available, Boehringer Ingelheim will review the benefit-risk-assessment and, if needed, pause or discontinue the trial treatment for all patients or take any other appropriate action to guarantee the safety of the trial patients.

Even if the trial treatment is discontinued, the patients remain in the trial and, given their agreement, will undergo the procedures for early treatment discontinuation and follow-up as outlined in the [Flow Chart](#) and [Section 6.2.3](#).

Treatment discontinuation

Patients with a fistula relapse will be discontinued from treatment if one of the following occurs:

- If patient has no clinical benefit after reinduction as per investigator judgement
- Fistula relapse with negative drug levels at the confirmation visit (with or without positive ADA).
- Occurrence of >2 confirmed fistula relapses within a 12 month period.

Patients can discontinue trial treatment at any time they feel they are losing the benefit from continuing treatment with the study drug.

Patients who terminate the study drug in 1368-0007 prematurely should complete an early EOT visit instead of the next planned visit followed by a safety follow up (EOS) visit 16 weeks after the last study drug intake.

3.3.4.2 Withdrawal of consent to trial participation

Patients may withdraw their consent to trial participation at any time without the need to justify the decision.

If a patient wants to withdraw consent, the investigator should be involved in the discussion with the patient and explain the difference between trial treatment discontinuation and withdrawal of consent to trial participation, as well as explain the options for continued follow-up after trial treatment discontinuation.

3.3.4.3 Discontinuation of the trial by the sponsor

Boehringer Ingelheim reserves the right to discontinue the trial overall or at a particular trial site at any time for the following reasons:

1. Failure to meet expected enrolment goals overall or at a particular trial site.
2. Emergence of any efficacy/safety information invalidating the earlier positive benefit-risk-assessment that could significantly affect the continuation of the trial.
3. Deviations from GCP, the trial protocol, or the contract impairing the appropriate conduct of the trial.

Further follow up of patients affected will occur as described in [Section 3.3.4.1](#).

The investigator/trial site will be reimbursed for reasonable expenses incurred in case of trial termination (except in case of the third reason).

4. TREATMENTS

4.1 INVESTIGATIONAL TREATMENTS

4.1.1 Identity of the Investigational Medicinal Products

Table 4.1.1:1 Spesolimab solution for s.c. injection

Substance:	Spesolimab, BI 655130
Pharmaceutical formulation:	Solution for injection
Source:	Boehringer Ingelheim Pharma GmbH & Co. KG
Unit strength:	Spesolimab 150mg/pre-filled syringes (150mg/mL)
Molecular weight	146 kDa
Unit strength	Spesolimab 150mg / syringe or vial (to be switched to 300mg when 2mL syringe or vials are available)
Posology:	300 mg at Week 0 and then every 4 weeks (2 injections every visit with 1mL syringes/ 1 injection when switching to 2ml device) 600 mg every 4 weeks as intensified treatment for patients with fistula relapse (4 injections every visit with 1mL syringes/ 1 injection when switching to 2ml device)
Mode of administration:	Subcutaneous injections

Table 4.1.1: 2 Spesolimab i.v. infusion

Substance:	Spesolimab, BI 655130
Pharmaceutical formulation:	Solution for infusion
Source:	Boehringer Ingelheim Pharma GmbH & Co. KG
Unit strength:	Spesolimab 300mg/vial (60mg/mL)
Posology:	1200 mg single dose in case of fistula relapse
Method and route of administration:	Intravenous infusion

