*Visit type F after visit M25: no blood and stool sampling for biomarkers

FLOWCHART 1C: END OF TREATMENT AND END OF STUDY VISITS

Trial Periods	M85/EOT	EOS¹²
Visit		
Week	336	352
Day	2353	2466
Visit Window (days)	+7	+7
eDiary		
Rectoscopy or proctoscopy		
Physical exam (including vital signs),weight ³	X ^c	X ^c
12 lead-ECG	X	X
Pregnancy test ⁴	X	X
Concomitant therapy	X	X
Adverse events ^{17, 19}	X	X
Safety laboratory test ⁶	X	X
QuantiFERON-TB test	X	X
Blood infection testing ²¹	X	
Study drug administration ¹²	X	
Contact IRT	X	
Local tolerability assessment	X	
Study completion		X

FLOW CHART 2A: PATIENTS WITH INFLAMMATORY FLARE WITH NO FISTULA RELAPSE

These visits will be done when the patient presents with a flare but no fistula relapse starting with flare confirmation visit, followed with visits F1 to F6, re-start at F1 and repeat visits type F1 to F6 until EOT or a new flare or fistula relapse occurs.

Naming convention will be i.e.: FL02V04F5: second flare, flare visit number 4, visit type 5
 Flare Confirmation number: FLn (luminal flare and fistula relapse will count as consecutive numbers)

Visit number: Vn (consecutive number of visits at each flare/relapse)

Visit type: from F1 to F6

Trial periods	Flare confirmation	Flare maintenance treatments					
		F1n	F1	F2	F3	F4	F5
Visit							
FLn							
Week (always count after last dose of of maintenance treatment) ²²	N.A.	4	8	12	16	20	24
Day ²²	N.A.	29	57	85	113	141	169
Visit Window (days)	N.A.	±7	±7	±7	±7	±7	±7
eDiary		█	█	█	█	█	
		█	█	█	█	█	█
Ileocolonoscopy+ [REDACTED], [REDACTED]	X			X			
Physical exam (with vital signs), weight ³	X ^T	X ^T	X ^T	X ^T	X ^T	X ^T	X ^T
12-lead ECG	X			X			X
Pregnancy test ⁴		X	X	X	X	X	X
Concomitant therapy	X	X	X	X	X	X	X
Adverse events ¹⁷	X	X	X	X	X	X	X
Safety laboratory tests ⁶	X	X		X		X	
	█						█
	█			█			█
	█			█			█
Stool sampling for enteric pathogens ¹⁵	X						
	█						█
Contact IRT	X	X	X	X	X	X	X
Study drug administration ²²		X	X	X	X	X	X
Local tolerability assessment		X	X	X	X	X	X

FLOW CHART 2B: FISTULA RELAPSE (WITH OR WITHOUT A LUMINAL FLARE)

These visits will be done when the patient presents with a fistula relapse, with or without luminal flare, starting with fistula relapse confirmation visit, followed by an IV reinduction visit and then visits F1 to F6, re-start at F1 and repeat visits type F1 to F6 until EOT or a new fistula relapse occurs.

Naming convention will be i.e.: FL02V04F5: second fistula, fistula visit number 4, visit type 5

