11. First study drug will be administered at M1.
12. For patients who discontinue study medication before scheduled end of treatment, an early EOT visit has to be scheduled. No treatment administration will be done at this visit. EOS visit will be 16 weeks after last dose of study medication.
13. For patients with inflammatory flares only, endoscopy (rectoscopy, proctoscopy, sigmoidoscopy, colonoscopy or full ileocolonoscopy) does not need to be repeated if done within 6 weeks prior to EOT visit.
14. Patients who develop a fistula relapse will receive a single infusion of 1200mg spesolimab i.v. followed 4 weeks later by intensified maintenance treatment with 600mg spesolimab s.c. q4W until the originally scheduled EOT visit (i.e. at week 336 after start of first sc. maintenance treatment)
15. Stool sampling for enteric pathogens only need at visit 1 and in case of inflammatory flare, according routine medical practice. If collection is not possible at visit 1, stool sample has to be collected at visit M1.
16. [REDACTED]
17. Please see [Section 5.2.6.2.1](#) for important instructions regarding AE collection in parent and extension trial further below
18. Quantiferon in all patients, either in maintenance [flowchart](#) or in case of flare/fistula relapse), will be tested every 48 weeks (aprox 1 year) from day 1 (visit M1), and at EOT and EOS.
19. After the EOS visit (individual patient's end of the trial) the investigator should report only any cancers of new histology and exacerbations of existing cancer (if applicable), trial treatment related SAEs and trial treatment related AESIs of which the investigator may become aware of and only via the BI SAE form for this extension trial , please see [section 5.2.6.2.1](#).
20. Visit types include all procedures that should be done at every type of visit from week 48(M13), see [flow chart 1B](#).
21. Infection testing for HBV (not HCV and HIV) to be repeated at EOT
22. Patients who present a luminal inflammatory flare (but NO fistula relapse) might receive standard of care treatment for flare as per investigator judgement, while continuing with their spesolimab maintenance dose of 300mg s.c. visit F1 will be done 4 weeks after last visit dosed, but not after flare confirmation visit.

TABLE OF CONTENTS

TITLE PAGE	1
CLINICAL TRIAL PROTOCOL SYNOPSIS	2
FLOW CHART 1.....	4
FLOWCHART 1A: V1, M1-M13	4
FLOWCHART 1B: M14-M84	6
FLOWCHART 1C: END OF TREATMENT AND END OF STUDY VISITS	7

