4.1.2 Selection of doses in the trial and dose modifications

This trial, 1368-0007, aims to offer a maintenance treatment for patients with perianal CD who have failed available therapies and whom are considered to have benefited from previous induction therapy in the parent trial.

The spesolimab subcutaneous dose regimen chosen for 1368-0007 has thus been selected with the objective of achieving maintenance of induction therapy effect with the safest profile based on available data from Phase I and Phase II studies in HV and patients with PPP and UC, respectively.

Bioavailability of the s.c. relative to the i.v. formulation of spesolimab is approx. 50%-70 % (cf. section 6.2 of IB [c03320877-08](#)). A subcutaneous dose of 300mg would therefore correspond to ~210 mg as an i.v. dose and thus represents the lowest dose of 3 mg/kg which was found to be fully active in the indirect target engagement assays in studies 1368-0001 and 1368-0002.

The dosing interval of every 4 weeks (q4w) was selected based on the half-life of approximately 4-5 weeks in healthy volunteers and PPP patients, as determined in the PoCC trial 1368-0015 and phase I studies 1368-0001 and 1368-0002, respectively. Thus, after one half life (~4 weeks) patients' exposure would drop below the threshold required to maintain maximal target engagement.

In patients experiencing a fistula relapse, a single 1200mg i.v. high treatment dose will be administered, followed by a maintenance dose of 600mg q4w, as defined in [Section 3.1](#) to double the exposure compared to the original failing maintenance regimen.

The loading i.v. dose of 1200mg is expected to be at the plateau of the dose/response curve and to provide maximal efficacy based on data indicating high and sustained target engagement at doses ≥ 3 mg/kg and a half-life as long as 4-5 weeks in healthy volunteers and PPP patients respectively (cf. sections 6.1 and 6.2 of the IB [c03320877-08](#)). This dosing regimen will achieve exposures below the highest dose regimen that was found safe in phase I studies. It therefore is also being tested in ongoing studies in IBD trials. These doses may be adapted later (via protocol amendment) based on emerging data from other trials with spesolimab.

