4.1.8 Drug accountability

The investigator or designee will receive the investigational drugs delivered by the sponsor when the following requirements are fulfilled:

- Approval of the clinical trial protocol by the IRB / ethics committee
- Availability of a signed and dated clinical trial contract between the sponsor and the investigational site
- Approval/notification of the regulatory authority, e.g. competent authority
- Availability of the curriculum vitae of the Principal Investigator
- Availability of a signed and dated clinical trial protocol
- Availability of the proof of a medical license for the Principal Investigator
- Availability of FDA Form 1572 (if applicable)

Investigational drugs are not allowed to be used outside the context of this protocol. They must not be forwarded to other investigators or clinics. Patients should be instructed to return unused investigational drug.

The investigator or designee must maintain records of the product's delivery to the trial site, the inventory at the site, the use by each patient, and the return to the sponsor or warehouse / drug distribution centre or alternative disposal of unused products. If applicable, the sponsor or warehouse / drug distribution centre will maintain records of the disposal.

These records will include dates, quantities, batch / serial numbers, expiry ('use- by') dates, and the unique code numbers assigned to the investigational medicinal product and trial patients. The investigator or designee will maintain records that document adequately that the patients were provided the doses specified by the Clinical Trial Protocol (CTP) and reconcile all investigational medicinal products received from the sponsor. At the time of return to the

sponsor <and/or> appointed CRO, the investigator or designee must verify that all unused or partially used drug supplies have been returned by the clinical trial patient and that no remaining supplies are in the investigator's possession.

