Rationale for change	Patient population is expected to have low endoscopic and [REDACTED] as per eligibility criteria (perianal disease and [REDACTED] < 250). Therefore, the chance for this small sample size study to reliable evaluate spesolimab effect on endoscopic inflammation beyond the rectum is very low. Hence, this clinical outcome will be explored but has been removed from main endpoints
Section to be changed	Section 2.1 and 3.1
Description of change	Definition of CD inflammatory flare.
Rationale for change	Changed [REDACTED] of flare to an absolute value instead of a change from baseline as there will not be ileocolonoscopy performed at screening.
Section to be changed	Section 3, Section 6.2.1, Section 6.2.2
Description of change	Ileocolonoscopy is not mandatory. Instead recto-or proctoscopy requested for screening and yearly afterwards [REDACTED] [REDACTED] for segment rectum. Ileocolonoscopy only mandatory as a confirmation of flare. .
Rationale for change	Ileocolonoscopy is not needed for eligibility purposes and neither for assessment of perianal activity. This patient population (perianal CD) is expected to have low inflammation scores as per eligibility criteria. Thus, the chance for this small sample size study to reliable evaluate spesolimab effect on endoscopic inflammation beyond the rectum is very low. Hence, this clinical outcome will be explored but there is no justification for a full ileocolonoscopy to be mandatory.
Section to be changed	Section 3.3.4.1
Description of change	Change of criteria for treatment discontinuation in case of flare/fistula.
Rationale for change	Leave the decision to terminate treatment to the investigator judgement, allowing the investigator to

		decide if there is clinical benefit for the patient instead of restricting the chance to continue to those who meet restricted definition of clinical response as per as a more global approach to patient clinical improvement, since these patients might not have other available options.
Section to be changed		4.1.1 Identity of the Investigational Medicinal Products
Description of change		Inclusion of number of injection/vial per dosis
Rationale for change		Clarification of posology
Section to be changed		Table 4.2.1.2:1 Restrictions regarding concomitant treatment
Description of change		Restriction for autologous or allogeneic haematopoietic (HSC) or mesenchymal stem cell (MSC) therapy
Rationale for change		Inclusion on restriction of a therapy

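### The dosing table calls for one 2 mL injection to deliver 600 mg, but the 2 mL device holds 300 mg, so two are needed

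*Protocol*

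**What the plan says.** Table 4.1.1:1 in Protocol Section 4.1.1 describes the subcutaneous product as a 150 mg/mL solution supplied at 150 mg per 1 mL unit, with the unit strength "to be switched to 300mg when 2mL syringe or vials are available". It then gives injection counts for the two subcutaneous doses:

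- 300 mg every 4 weeks (standard maintenance): "2 injections every visit with 1mL syringes/ 1 injection when switching to 2ml device".
- 600 mg every 4 weeks (after fistula relapse): "4 injections every visit with 1mL syringes/ 1 injection when switching to 2ml device".

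Section 4.1.2 gives the purpose of the 600 mg regimen, which follows a single 1200 mg infusion: "to double the exposure compared to the original failing maintenance regimen". Flow chart footnote 14 prescribes "intensified maintenance treatment with 600mg spesolimab s.c. q4W until the originally scheduled EOT visit". The synopsis, Protocol Section 3.1 and SAP Section 6.1 also give 600 mg. The log for Global Amendment 1 (Protocol Section 11.1) records the change to Section 4.1.1 as "Inclusion of number of injection/vial per dosis", made to clarify posology.

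**The concern.** Both doses carry the same count for the 2 mL device, although one is twice the other. One of the two counts has to be wrong, and the unit-strength row shows that it is the one for 600 mg.

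The affected patients are those with a confirmed fistula relapse. If one 2 mL device is given, their subcutaneous dose stays at 300 mg, the dose that Section 4.1.2 intends to double. Under Section 3.3.4.1 these patients are taken off treatment if the investigator sees no clinical benefit after reinduction, or after more than two confirmed relapses in 12 months. An underdosed patient could therefore be counted as a failure of a regimen that was never given.

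A half dose might also be hard to notice. Section 4.3 asks for missed doses to be documented and reported but does not mention partial ones, and SAP Section 7.3 drops compliance reporting. That leaves the accountability records of Section 4.1.8.

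**Working it through.** **Inputs**, all from Table 4.1.1:1 unless stated:

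- Concentration: 150 mg/mL.
- 1 mL unit: 150 mg. 2 mL unit: 300 mg.
- Doses: 300 mg and 600 mg every 4 weeks.
- Subcutaneous visits in one relapse cycle: six, F1 to F6 at weeks 4 to 24. In Flow Chart 2B the relapse confirmation visit is "followed by an IV reinduction visit and then visits F1 to F6".

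**Formula.** Injections needed = dose ÷ (concentration × device volume).

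| Dose | Device | Device holds | Needed | Stated | Delivered by stated count |
|---|---|---|---|---|---|
| 300 mg | 1 mL | 150 mg | 300 ÷ 150 = 2 | 2 | 300 mg |
| 300 mg | 2 mL | 300 mg | 300 ÷ 300 = 1 | 1 | 300 mg |
| 600 mg | 1 mL | 150 mg | 600 ÷ 150 = 4 | 4 | 600 mg |
| 600 mg | 2 mL | 300 mg | 600 ÷ 300 = 2 | **1** | **300 mg** |

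Three of the four counts reproduce. The fourth does not: 600 ÷ 150 = 4 mL, which cannot come from one 2 mL device.

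**Could another reading save it?** A single 2 mL injection of 600 mg would need 600 ÷ 2 = 300 mg/mL, a strength that the subcutaneous table does not list. The table also states 300 mg for the 2 mL unit directly, so the result does not rest on assuming that the concentration stays the same. If *vial* means drawing several vials into one injection, two vials are still needed and the row does not say so.

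**Size.** Per affected visit: 300 mg given against 600 mg intended, or (300 − 600) ÷ 600 = −50%. Over one F1–F6 cycle, 6 × 600 = 3,600 mg is intended. If k of the six visits follow the count, 3,600 − 300k mg is given:

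- k = 0: 3,600 mg, no shortfall (for example, the 2 mL device is never used).
- k = 3: 2,700 mg.
- k = 6: 1,800 mg.

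The six-visit cycle is only for illustration. F1 to F6 repeat until end of treatment or a new relapse, so a total shortfall could be larger. The −50% per visit is the stable figure.

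**Reach into the analysis.** The primary endpoint (Protocol Section 7.2.2) divides patients with an event by time at risk and uses no milligrams. The current SAP pools all treatment under the single Overall Speso label (Section 6.1) and replaces the secondary endpoint analyses with a patient listing (Section 4). Only the total subcutaneous milligrams in SAP Section 7.7 could be misstated, and only if they are computed from the nominal dose.

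**The case against.** The arithmetic is not in dispute. The case on the other side is that the slip is minor:

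- The correct dose, 600 mg, stands in the same cell as the wrong count and is repeated through both documents. The 300 mg unit strength is in the same table, so a careful reader would see the conflict.
- Other controls stand between the table and the patient. Medication is assigned through IRT, injection instructions are in the investigator site file (Section 4.1.4), dosing is supervised (Section 4.3), and product is reconciled against the protocol dose (Section 4.1.8).
- Nothing shows that the 2 mL device was ever supplied.
- No endpoint result is shown to change.
- The current SAP (Sections 3 and 10) describes a trial that the sponsor has ended early, so correcting the dosing text may now have little practical use.

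Most of this stands as a limit on the consequences. The documents do not show that any patient was misdosed, and the termination matters for what can still usefully be done. None of it makes the count right. The site file and IRT quantities are not available to check, so they cannot be relied on to have caught it. The amendment log also shows that the counts were added to clarify posology, so they were put there to be used.

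**Conclusion.** The count is wrong as written in the current protocol (Version 3.0). The 600 mg dose needs two 2 mL devices, and the one stated delivers 300 mg, a 50% shortfall at each affected visit. This follows from the table alone and needs no outside assumption.

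Any effect on patients depends on two things that the documents do not settle: that the 2 mL device was introduced, and that staff or the dispensing system followed the count rather than the stated dose. If either fails, the shortfall is zero. The planned dose itself is not in doubt, and the possible effect on the reported analysis is confined to the subcutaneous milligram exposure table. Even so, a posology row that can halve a dose should be corrected before the device it refers to is used.

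**What to change.** 1. In the 600 mg row of Table 4.1.1:1, change the 2 mL device count from one injection to two.
2. Before the 2 mL device is used, confirm that the site file instructions and the IRT dispensing quantity supply two devices for each 600 mg dose.
3. Because the trial has been stopped, establish whether any 600 mg visit used the 2 mL device. If so, derive the subcutaneous milligrams for SAP Section 7.7 from what was actually used and not from the nominal dose. Section 4.1.8 already requires the data: "These records will include dates, quantities, batch / serial numbers".

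The cost is one number in the protocol and a check of existing instructions and records. No new procedure or data collection is needed.
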